12.7.3.1 Potential Drug-induced Liver Injury (DILI)

Liver function test data will also be provided in separate listings for:

- Patients who possibly met Hy's Law criteria (i.e., had any elevated ALT or AST of $> 3 \times$ ULN, and increase in total bilirubin $\geq 2 \times$ ULN, at the same visit)
- Patients who met any one or more of the following criteria at any post-baseline visit (list laboratory parameters ALT, AST, and total bilirubin only)
- ALT or AST $> 3 \times$ ULN with the appearance of fatigue, nausea, vomiting, right upper quadrant pain or tenderness, fever, rash, and/or eosinophilia ($> 5\%$)
- ALT or AST $> 8 \times$ ULN
- ALT or AST $> 5 \times$ ULN for more than 2 weeks
- ALT or AST $> 3 \times$ ULN and (TBL $> 2 \times$ ULN or INR > 1.5)

A summary table will also be provided by treatment arm for number of patients who met any of the criteria specified above at any post-baseline visit. Any elevation during the wash-out period will be linked to the actual treatment arm received during Period 1 whereas any elevation observed permanent treatment discontinuation will be linked to the last treatment received.

A drug-induced serious hepatotoxicity (DISH) plot will display, for each patient during each 21-day on-treatment safety period (as defined in [Section 10.1.1](#)) the maximal total bilirubin value (expressed as a multiple of the ULN) against the maximal ALT value (expressed multiple of the ULN) to identify possible Hy's Law range or Temple's Corollary.

All post-baseline potential drug-induced liver injury laboratory data will be listed.

12.7.4 Vital Signs

Vital signs will include sitting SBP and DBP and pulse rate which are planned to be measured at Day 1 H0, D1H3, Day 15 and D21 of each treatment period as well as during the screening and the FU visit.

Vital signs parameters will be summarized on the Safety Analysis Set as described below.

Observed and change from baseline value in vital signs measures at each scheduled timepoint (D1H3, Day 15, D21) will be summarized by treatment arm.

The number and percentage of patients with any clinically significant abnormal value and change in vital signs (as defined in Appendix 6) within each treatment period will be summarized by treatment arm within the Safety Analysis Set.

Observed and change from baseline (Screening) to FU will also be summarized by treatment sequence.

All vital signs data will be listed.

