9.2.10 Vital Signs

As part of the screening procedures at Visit 1, vital signs (systolic and diastolic blood pressure and pulse rate) will first be measured after the patient assumed a supine position for 5 minutes. Vital signs will then be measured within 2 minutes of assuming a standing position in ambulatory patients only. At all subsequent time points, vital sign

measurements will be completed in a sitting position at rest for 5 minutes. Blood pressure should be recorded using the same arm throughout the trial, where possible.

Additional vital signs measurements may be taken during the trial if clinically indicated.

9.2.11 12-Lead Electrocardiogram

A 12-lead ECG will be performed after 5 minutes in a supine position. A physician must review the ECG (annotated, signed, and dated) and any abnormal findings considered to indicate significant medical history or AEs must be recorded appropriately on the eCRF. Additional ECG measurements can be taken at any time during the trial, if clinically indicated.

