- the reference day for Period 1,
- the reference day for Period 2,

For clinic-safety based endpoints, baseline is defined as the last record or measure collected prior to the first dose of IMP or if deemed necessary as the reference day as described in [Section 10.1.2](#).

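### The vital-sign change from Screening to follow-up may compare different postures, because the documents disagree on whether a sitting Screening reading exists; the sitting Day 1 predose value avoids the problem.

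*SAP*

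**What the plan says.** - **Planned table.** SAP 12.7.4 (Vital Signs): "Observed and change from baseline (Screening) to FU will also be summarized by treatment sequence".
- **Measurement procedure.** Protocol 9.2.10: the Visit 1 procedure opens with "vital signs (systolic and diastolic blood pressure and pulse rate) will first be measured after the patient assumed a supine position for 5 minutes", followed by "Vital signs will then be measured within 2 minutes of assuming a standing position in ambulatory patients only". At every later time point, "measurements will be completed in a sitting position at rest for 5 minutes". Protocol 9.1.5 includes vital signs at the Safety Follow-up Visit (Visit 10), so that reading is sitting.
- **Baseline table.** SAP 12.2.3 lists supine values and supine-minus-standing differences. It has no sitting value.
- **Opening of SAP 12.7.4.** "Vital signs will include sitting SBP and DBP and pulse rate which are planned to be measured at Day 1 H0", and the list of time points ends with "as well as during the screening and the FU visit".
- **Eligibility.** Protocol exclusion criterion 6.2.12 sets its blood-pressure limits on a sitting reading and names Visit 1 or Visit 2.
- **General safety baseline.** SAP 10.2, for clinic-based safety endpoints: "baseline is defined as the last record or measure collected prior to the first dose of IMP or if deemed necessary" the reference day of SAP 10.1.2, which is the day of first dose.

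**The concern.** A change score is interpretable only if both readings were taken in the same way. If protocol 9.2.10 is what sites follow, the follow-up reading is sitting and the Screening reading is not. The reported mean change then contains a posture component as well as any change over the trial, and a reader of the table could not separate the two.

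The label also departs from the SAP's own rule. The last measure before first dose is ordinarily the Day 1 predose reading, not Screening. The visit windows in SAP 10.1.3 treat Screening and Day 1 H0 as separate analysis visits, so the word Screening cannot simply be read as Day 1 predose.

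What is at stake is the readability of one planned safety table. Efficacy analyses and sample size are not touched.

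**Working it through.** The plan gives no figure to reproduce, so the check sets the texts side by side and adds one identity.

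**Step 1. Posture at each end of the subtraction.**

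| Source | Visit 1 (Screening) | Day 1 predose | Follow-up |
|---|---|---|---|
| Protocol 9.2.10 | supine, then standing if ambulatory | sitting | sitting |
| SAP 12.2.3 | supine and supine minus standing | not listed | not listed |
| SAP 12.7.4, opening sentence | sitting | sitting | sitting |
| Exclusion 6.2.12 | sitting reading implied at Visit 1 or Visit 2 | sitting reading implied at Visit 1 or Visit 2 | not applicable |

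The first two sources agree with each other, and the last two point the other way at Visit 1. No source puts Day 1 predose or follow-up in any posture but sitting. Vital signs are scheduled predose at Visit 2 (protocol 9.1.2.1), so the sitting Day 1 value is already collected.

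**Step 2. What the table would contain under each reading.**
- Supine Screening subtracted: all patients contribute, with mixed posture.
- Standing Screening subtracted: mixed posture, and only ambulatory patients contribute.
- Sitting records only, at sites following protocol 9.2.10: there is no Screening value, so the change column is empty.
- A sitting Screening reading actually collected: like for like, with no posture problem.

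The change-to-follow-up sentence in SAP 12.7.4 does not name the Screening posture to be used.

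**Step 3. How an offset enters.** Let FU be the follow-up reading (sitting), D1 the Day 1 predose reading (sitting) and SCR the Screening reading (supine or standing). Then

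FU − SCR = (FU − D1) + (D1 − SCR).

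The first bracket is the like-for-like change. The second is the posture offset P plus any true change between Screening and Day 1. Averaging within a sequence keeps the same form, so P passes into the mean change with coefficient 1.

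The documents give no value for P. Purely as an assumption, P of 0, 5 or 10 mmHg in either direction would move each sequence's mean change by that same 0, 5 or 10 mmHg.

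**Step 4. Between sequences.** Write the mean changes as C1 + P and C2 + P, where C1 and C2 are the two sequences' mean changes apart from posture. Their difference is C1 − C2. Sequence is randomized, so P is expected to be equal in both and to cancel, apart from chance imbalance. It does not cancel in the within-sequence means that the table reports.

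**Step 5. By-arm on-treatment changes.** SAP 12.7.4 also summarizes change at D1H3, Day 15 and D21 by treatment arm, from baseline without the Screening qualifier. Under SAP 10.2 that baseline is the last predose record, which is sitting provided the Day 1 predose reading was taken. Both terms are then sitting.

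**The case against.** The strongest reply is that SAP 12.7.4 itself says sitting readings are planned at screening. Taken alone, the disputed sentence then subtracts sitting from sitting, and criterion 6.2.12 supports that. This stands to the extent that a mixed-posture subtraction is not established as the plan; what is established is a contradiction. It does not settle the matter, because protocol 9.2.10 describes the measurement procedure without any sitting reading at Visit 1, the SAP's baseline table agrees with it, and a sitting reading for 6.2.12 is available at Visit 2.

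A second reply is that a change over the whole study may be intended, since SAP 12.7.5.1 also uses Screening to follow-up for weight although a Day 1 weight exists. That is possible. The posture question does not arise for weight, however, so the analogy does not resolve it for blood pressure and pulse.

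Two stronger readings are tempting, and the documents do not support them:
- **That the table could hide or mimic a drug effect.** It is by sequence, and completers in both sequences have received both treatments. Follow-up is at least 7 days after the last dose (protocol 9.1.5), and SAP 10.1.1 adds no days after end of treatment to the on-treatment window for vital signs. The table does not estimate a nabiximols–placebo contrast. The protocol's endpoint of change by treatment period is served by the by-arm summaries, which are unaffected.
- **That the offset can be scaled against the 20 mmHg and 10 bpm change criteria in SAP Appendix 6.** Those are patient-level criteria that also require an absolute value to be met, and SAP 12.7.4 applies them within each treatment period. They are not applied to this mean change.

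**Conclusion.** The point holds as a minor one. The documents contradict each other on whether a sitting Screening reading exists. If protocol 9.2.10 and SAP 12.2.3 describe what is collected, the Screening-to-follow-up change either mixes postures, with any offset entering each sequence's mean one for one, or has no sitting value to subtract. Under any reading, the Screening label departs from the SAP's last-predose safety baseline.

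The size cannot be given from the documents. The reach is limited to one additional descriptive, off-treatment, by-sequence safety table. The expected cancellation between sequences rests on randomization and on the same Screening posture being used in both. The statement that the by-arm changes are unaffected rests on the Day 1 predose reading being present and sitting.

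**What to change.** 1. In SAP 12.7.4, define baseline for the change to follow-up as the sitting Period 1 Day 1 predose (H0) value. It is sitting under every reading of the documents and agrees with SAP 10.2.
2. Keep the Visit 1 supine and standing values in the orthostatic baseline table of SAP 12.2.3.
3. Reconcile protocol 6.2.12, protocol 9.2.10, SAP 12.2.3 and SAP 12.7.4 on the posture used at Visit 1.

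The change to the table is one phrase and needs no new data; the reconciliation is a wording correction. The one small loss is that the table no longer spans the screening period. If a whole-study change is wanted, the SAP should state that a sitting Screening reading is collected and is the one subtracted.

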12.7.5 Physical Examination, ECGs and other Observation Related to Safety

12.7.5.1 Physical Examination: Weight and BMI

Weight is planned to be measured at Screening, Day 1H0 of each period and at follow-up visit.

Based on the Safety Analysis Set, weight and BMI (as defined in [Section 10.11](#)), observed and change from baseline value at each scheduled timepoint (Period 2 Day 1 H0, D21) will be summarized by treatment arm.

Observed and change from Screening to FU will also be summarized by treatment sequence.

The number and percentage of patients meeting a clinically significant change in weight (as defined in [Appendix 6](#) at any time during) within each treatment period will be summarized by treatment arm. All measurements (scheduled or unscheduled) will be used to determine if any abnormality criteria is met (as determined in Appendix 6).

Weight and BMI will be listed.

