Control Arm	All patients enrolled in the trial will receive both nabiximols and placebo during the 2-way crossover treatment period.

Procedures	
Assessments/procedures at the trial site include the following:
 
• Informed consent, demographics, previous cannabis use, medical history, electronic diary training, and blood THC test (Visit 1)• Eligibility check and urine drug screen (including THC) (Visits 1 and 2 [predose])• Randomization and IMP dosing training (Visit 2 [predose])• Concomitant medications review, AE review, and vital signs measurement (Visits 1, 2, 4, 5, 6, 8, 9, and 10)• Physical examination (including height measurement at Visit 1 only), 12-lead ECG, and clinical laboratory blood sampling (hematology and biochemistry) (Visits 1, 5, and 9)• Examination of oral mucosa (Visits 1, 2 [predose], 4, 5, 6 [predose], 8, 9, and 10)• Body weight measurement (Visits 1, 2 [predose], 6 [predose], and 10)• Dipstick urinalysis and serum pregnancy test (if appropriate) (Visits 1 and 10)• Urine pregnancy test (if appropriate) (Visits 2 and 6 [predose])• PK blood sampling (IMP) at distinct time points (Visits 2, 4, 5, 6, 8, and 9)• MAS assessment (Visits 1, 2 [predose and at 3 hours ± 15 minutes postdose], 5 [3 hours ± 15 minutes after the first spray of the morning dose], 6 [predose and at 3 hours ± 15 minutes postdose], and 9 [3 hours ± 15 minutes after the first spray of the morning dose])• MSSS-88 assessment (Visits 5 and 9)• T25FW test (Visits 2 [predose], 5, 6 [predose], and 9)• C-SSRS assessment (Visits 1, 2 [predose], 4, 5, 6 [predose], 8, 9, and 10)• IMP dosing at the investigational site (Visits 2, 5, 6, and 9)• IMP dispensing (Visits 2, 4, 6, and 8)• IMP collection and compliance review (Visits 4, 5, 8, and 9)
------------	--

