10.0 Conventions and Derivations

10.1 Study Period, Reference Day, Study Day, Analysis Day and Visit Window

10.1.1 Study Periods

For each patient, there will be a screening period, an evaluable period composed of a treatment period 1, a washout period, and a treatment period 2, and a safety follow-up period.

The Screening period starts on the day of the informed consent signature and ends on Day 1 (as defined on in [Section 10.1.2](#)) before 1st IMP intake.

The evaluable period starts on the day of randomization and ends the day of the safety follow-up visit.

- The **51-day efficacy period** which starts on the first day of IMP administration and ends at the end of treatment date.
 - This period will be composed of:
 - The **21-day on-treatment efficacy Period 1** which starts the day of first IMP intake during Period 1 and ends the earliest between end of Period 1 D21 date and permanent end of treatment date;
 - The on-treatment **wash-out period** which begins the day following the end of the 21-day on-treatment efficacy Period 1 and ends the day before the beginning of the 21-day on-treatment efficacy Period 2;
 - The **21-days on-treatment efficacy Period 2** which starts the day of IRT call for Period 2 and ends on the end of treatment date. This period is only defined for patients exposed to IMP during Period 2.
 - It will be used for efficacy analyses using the Full Analysis Set.
- The **51-day safety period** which starts on the first day of IMP administration and ends at the end of treatment date (+ x days).
 - This period will be composed of:
 - The **21 day on-treatment Safety Period 1** which starts the day of first IMP intake during Period 1 and ends the earliest between end of the wash out period date, the day before the date of IRT call for Period 2, the day before Visit 6 date and permanent end of treatment date + x days.
 - The **21 day on-treatment Safety Period 2** which starts the earliest between date of Visit 6, day of IRT on treatment safety period call for Period 2 date, and ends on the end of treatment day date + x days.
 - x will be equal to 14 days for Adverse events, 4 days for C-SSRS and 0 days otherwise.
 - it will be used for safety analyses using the Safety Analysis Set (unless otherwise specified).
- The **Follow-up period** which starts the day following the 51-day on-treatment safety period and ends on the end of study date.

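### SAP 12.7.5.1 lists a Day 21 weight that is not scheduled, and the SAP's date rules would label the Visit 6 predose weight change with the Period 2 treatment

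*SAP*

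**What the plan says.** SAP 12.7.5.1 first gives the schedule: "Weight is planned to be measured at Screening, Day 1H0 of each period and at follow-up visit". The protocol synopsis agrees: "Body weight measurement (Visits 1, 2 [predose], 6 [predose], and 10". The protocol's visit lists also agree. Sections 9.1.2.1 (Visit 2), 9.1.4.1 (Visit 6) and 9.1.5 (Visit 10) include weight; sections 9.1.2.3 (Visits 4 and 5) and 9.1.4.3 (Visits 8 and 9) do not.

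The next statement in SAP 12.7.5.1 is that weight and BMI, "observed and change from baseline value at each scheduled timepoint (Period 2 Day 1 H0, D21) will be summarized by treatment arm". Change from Screening to follow-up is summarised separately, by sequence. The count of patients with a clinically significant weight change (7% or more in either direction, SAP Appendix 6) "within each treatment period will be summarized by treatment arm", using scheduled and unscheduled weights.

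SAP 12.7 bases safety analyses on the on-treatment safety period by actual arm. SAP 10.1.1 ends Safety Period 1 at the earliest of several dates, among them "the day before the date of IRT call for Period 2, the day before Visit 6 date". Safety Period 2 is the one "which starts the earliest between date of Visit 6, day of IRT on treatment safety period call for Period 2 date". The extension after end of treatment is set by: "x will be equal to 14 days for Adverse events, 4 days for C-SSRS and 0 days otherwise".

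**The concern.** There are two separate problems. The first is an internal contradiction: one sentence omits Day 21 from the weight schedule, and the next lists it as a scheduled timepoint.

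The second concerns attribution. Without D21, the only scheduled post-baseline weight left in the by-arm summary is the one taken at Visit 6 before dosing. It can only reflect Period 1 treatment and the washout, but the SAP assigns data to periods by date, with no exception for predose values. A programmer applying those rules would report weight change that accrued on nabiximols in the placebo column, and the reverse. At stake is a by-arm safety table, and the matching 7% flag, that could point in the wrong direction.

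**Working it through.** There is no stated figure to reproduce, so the check places each scheduled weight on the nominal calendar and applies the SAP rules.

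**Inputs**
- First dose Day 1; last Period 1 dose the morning of Day 21 (protocol 8.2).
- Visit 6 predose on Day 31 (protocol 9.1.4.1).
- Last dose the morning of Day 51 (protocol 9.1.4.3); Visit 10 on Day 58 (protocol 9.1.5).
- x = 0 for weight (SAP 10.1.1).
- Default safety baseline: last value before the first dose in the trial, nominally Visit 2 predose (SAP 10.2).
- Period 2 analysis days count from the first Period 2 dosing date (SAP 10.1.2); SAP Table 10.1-1 files Visit 6 under Period 2, Day 1.

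**Period boundaries**
- Safety Period 1 ends by Day 31 − 1 = Day 30.
- Safety Period 2 starts by Day 31 and ends on Day 51 + 0 = Day 51.

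| Scheduled weight | Nominal day | Where the rules place it | Drug taken since the previous weight | By-arm label |
|---|---|---|---|---|
| Screening | −28 to −1 | before treatment | none | none |
| Visit 2 predose | 1 | baseline | none | baseline |
| Visit 6 predose | 31 | Safety Period 2 | Period 1 drug | Period 2 drug |
| Visit 10 | 58 | after Safety Period 2 | Period 2 drug | none (by sequence only) |

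**Result under the default baseline**
- Scheduled post-baseline weights per patient: 0 in Safety Period 1 and 1 in Safety Period 2.
- That one weight follows 0 doses of the Period 2 drug and comes 31 − 21 = 10 days after the last Period 1 dose.
- Its change from Visit 2 predose covers 31 − 1 = 30 days: Period 1 plus washout.
- In the nabiximols/placebo sequence the change accrued on nabiximols and is labelled placebo. In placebo/nabiximols it accrued on placebo and is labelled nabiximols.
- The 7% flag behaves in the same way where it rests on scheduled weights.
- The Visit 10 weight has no arm, so Period 2 has no scheduled by-arm change.

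**Result under the alternative baseline**
SAP 10.2 also allows the reference day as safety baseline if deemed necessary, and SAP 10.1.2 defines one for each period. Applied per period, Visit 6 predose becomes the Period 2 baseline, with change zero by definition. Period 1 has no scheduled weight after its own baseline up to Day 30, and Visit 10 is still outside Safety Period 2. No scheduled by-arm weight change can then be produced in either period.

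**Comparison with other safety data**
The SAP links washout findings to the Period 1 treatment for adverse events (12.7.1), liver elevations (12.7.3.1) and unscheduled C-SSRS (12.7.5.3). It links follow-up C-SSRS and liver elevations after permanent discontinuation to the last treatment received. Weight has no such rule, and by date Visit 6 comes after the washout has ended.

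**The case against.** The best defence is that 12.7.5.1 never says which arm the Visit 6 weight belongs to. A predose value listed as a change from baseline could well have been meant as the Period 1 outcome, which would match the handling of other findings between periods. D21 may simply have been carried over from the vital signs section (12.7.4), where it is a valid timepoint.

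Part of this stands. The mislabelling is inferred from the date rules and is not stated in 12.7.5.1. The intended rule is not written anywhere, however, and the rules that are written give the opposite result. The D21 contradiction is there on any reading.

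Three stronger readings are tempting, and the documents do not support them:
- A reader might infer that every by-arm 7% flag comes from the wrong period. Unscheduled weights also feed the flag, and one taken during a treatment period would be placed there correctly. The error is limited to flags resting on scheduled weights.
- A reader might infer that the Visit 10 weight is lost. It is summarised by sequence as change from Screening, and all weights are listed. What is missing is a by-arm Period 2 change.
- A reader might infer that the SAP definitely credits weight change to the wrong drug. It does so only if the date rules are followed literally with the default baseline. Under a per-period baseline nothing is credited to the wrong drug, because there is no scheduled by-arm change to report.

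**Conclusion.** The point holds in this limited form. The D21 entry contradicts the schedule in both documents. Under the date rules and the default safety baseline, the single scheduled by-arm weight change for each patient who reaches Visit 6 accrued on one treatment and would be labelled with the other. Period 2 has no scheduled by-arm change. Under the per-period baseline option, neither period has one.

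This assumes the nominal visit calendar, with Visit 6, the Period 2 IRT call and the first Period 2 dose on the same day, and period assignment by date as written. It does not rely on the visit windows in SAP Table 10.1-2, which should be checked for consistency when the text is corrected.

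The importance is low. Weight and BMI are descriptive safety outputs, no hypothesis test uses them, and efficacy conclusions are unaffected. It is still worth correcting, because a by-arm table with the treatments exchanged is worse than none.

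**What to change.** In SAP 12.7.5.1:
- Delete D21 from the weight and BMI timepoints.
- Attribute change from Visit 2 predose to Visit 6 predose to the Period 1 treatment.
- Attribute change from Visit 6 predose to Visit 10 to the Period 2 treatment.
- For patients who never enter Period 2, use change from Visit 2 predose to Visit 10, attributed to the Period 1 treatment.
- Apply the same baseline and attribution to the 7% flag for scheduled weights.

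The cost is SAP wording and the matching programming; every weight needed is already scheduled. The two intervals are of similar nominal length: 31 − 1 = 30 days and 58 − 31 = 27 days. The downside is that both include time off drug: nominally 10 days before Visit 6, and 7 to 10 days before Visit 10. A table footnote should say so. A simpler alternative is to report weight by sequence only, but the planned Screening to follow-up change mixes both treatments.
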